Subjects will undergo regular clinical examination, including measurement of visual acuity, intraocular pressure, slit lamp examination by their physician, and visual field testing as indicated. When it comes time to perform visual field testing, subjects will be randomized to complete either the Pico VR Headset visual field test first followed by the Humphrey Field Analyzer visual field test, or vice versa. Visual field tests will be separated by a rest period of one hour to minimize testing fatigue.

The Smart System VR Headset is fit to subjects' head using an adjustable head strap. Once the headset it fit to the subject, a research assistant will send a test to the headset from a bluetooth-connected electronic device using M&S Technologies' secured application platform. Subjects will follow prompts from the Smart System VR Headset to complete their visual field test, responding using a handheld "trigger" device. Testing is expected to take approximately 5-10 minutes, depending on the subjects' severity of visual field loss. Following visual field testing using both the Smart System VR Headset and Humphrey Field Analyzer, subjects will complete a 13-question satisfaction survey. The total expected time commitment of this study is an additional 1.5-2 hours to the subjects' regular clinical appointment.

M&S Technologies is the developer of the Smart System VR Headset visual field test. [name], [name], and [name] have no financial or intellectual relationship with M&S Technologies, aside from the current study and an additional study under IRB review investigating the EyeSimplify visual field test.

As the developers of the Smart System VR Headset visual field test, M&S Technologies maintains a secure, encrypted, HIPAA-compliant database of Smart System VR Headset users. This database includes patient profiles containing unique subject IDs (de-identified), birth year, and visual field testing results. Outside of this testing information, M&S Technologies does not have access to any additional patient information.

1.5 Specify your research question(s), study aims or hypotheses (do not indicate "see protocol")

Aim 1: Compare the performance of the Smart System VR Headset to the Humphrey Visual Field Analyzer

Aim 2: Determine the subjective perception of ease of use of the Smart System VR Headset

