nuclear medicine therapy)?

No

V.20 Does this project involve the deliberate transfer of recombinant or synthetic nucleic acid molecules, or DNA or RNA derived from recombinant or synthetic nucleic acid molecules, into one or more human research participant?

No

V.21 Will any portion of this project be conducted in the CRU, or does it use any CRU resources?

V.22 Will this project use:

- any resource/patients of the Holden Comprehensive Cancer Center
- involve treatment, detection, supportive care, or prevention of cancer

No

V.25.a Will the study involve any of the following activity at UI Health Care, even if subjects or their insurance will not be billed for the item or service, and regardless of the study funding source (including studies with departmental or no funding)?

- Procedures, tests, examinations, hospitalizations, use of Pathology services, use of clinic facilities or clinical equipment, or any patient care services, including services conducted in the Clinical Research Unit; or
- Physician services or services provided by non-physicians who are credentialed to bill (ARNPs, Physician Assistants, etc.)

Yes

V.25.b Will there be any procedures or services that may happen as part of a subject's regular medical care and as part of the study?

Yes

V.25.c Will any study equipment or devices be supplied by a study sponsor?

No

V.25.e Is there or will there be an internal budget for this study?

No

V.25.f Is there or will there be an external budget for this study?

No

V.26 The study involves Department of Nursing Services and Patient Care nursing, nursing resources or evaluates nursing practices at UI Health Care.

Νc

V.27 Will the study involve the use of the I-CTMS (OnCore) for clinical trial data management? Select yes if any or all of the following apply:

- Any study required to register subjects in EPIC are encouraged to use the I-CTMS
- Best practice is to use the I-CTMS for any new study that involves subject tracking or sponsor invoicing

Note: This question is for non-oncology studies only. For oncology studies use existing HCCC OnCore processes by selecting V.22

No

VI. Subjects

VI.1 How many adult subjects do you expect to consent or enroll for this project?

52

VI.2 What is the age of the youngest adult subject?

18.0

VI.3 What is the age of the oldest adult subject?

100.0

VI.4 What is the percentage of adult male subjects?

50

	VI.5	What is the percentage of adult female subjects? 50

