VI.6	How ma 0	ny minor subjects do you expect to consent or enroll for this project?
VI.13	Describe	EACH of your subject populations
		clude description of any control group(s) ecify the Inclusion/Exclusion criteria for EACH group
	Inclusion	criteria: Patients older than 18 years of age with suspected, mild, moderate, or severe glaucoma
	corrected	n criteria: Non-english speakers, patients with systemic or ocular disease affecting central vision (including best visual acuity less than 20/80), neurocognitive or psychiatric patients that are unable to perform testing, sm >+2.00/-2.00 diopters
VI.14		un estimate of the total number of subjects that would be eligible for inclusion in each of your study populations your control population if applicable)
VI.15		how you will have access to each of your study populations in sufficient number to meet your recruitment
		at the University of Iowa Hospitals and Clinics' Glaucoma clinic will be approached at the time of their scheduled aents to participate in this research study.
VI.16	Do you p No	elan to recruit/enroll non-English speaking people?
VI.18	Do you p	propose to enroll any of the following in this study as subjects?
	• Inc	uployee of the PI or employee of a research team member dividual supervised by PI or supervised by member of research team dividual subordinate to the PI or subordinate to any member of the research team udent or trainee under the direction of the PI or under the direction of a member of the research team
	No	
VI.20	Will subj No	ects provide any information about their relatives?
VI.23	Will any No	one (other than the subject) provide you with information about the subject (e.g. proxy interviews)?
VI.26	Is this pr No	oject about pregnant women?
VI.27	Will this No	project involve fetuses?
VI.28		s project involve adult subjects who may be incompetent or have limited decision-making capacity on initial int into the study?
VI.32	Does this No	s project involve subjects whose capacity to consent may change over the course of the study?

VII.A. Project Description (A)

No

VI.37

VII.A.1 Where will project procedures take place (check all that apply)?

Does this project involve prisoners as subjects?

• UIHC - Glaucoma clinic

VII.A.2 Is this project also being conducted by other researchers at their own sites (e.g. a multi-site collaborative project)?

No

VII.B. Project Description (B)

VII.B.

VII.B.1.

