• 🗸	Repository – The collection, storage, and distribution of human biologic samples and/or data materials for research purposes. Repository activities involve three components: (i) the collection of data and/or specimens such as blood, tissue, saliva, etc.; (ii) the storage of data or specimens, and data management function; and (iii) the sharing of data/specimens with recipient investigators other than the original investigators. (paraphrased from OHRP)
•	Other
1.a i	Does this project involve any of the following (Check all that apply):
	• Phase I trials – include initial studies to determine the metabolism and pharmacologic actions of drugs in humans, the side effects associated with increasing doses, and to gain early evidence of effectiveness; may include healthy participants and/or patients (ClinicalTrials.gov & FDA)
	• Phase II trials – include controlled clinical studies conducted to evaluate the effectiveness of the drug for a particular indication or indications in patients with the disease or condition under study and to determine the common short-term side effects and risks(ClinicalTrials.gov & FDA)
	• Phase III trials — include expanded controlled and uncontrolled trials after preliminary evidence suggesting effectiveness of the drug has been obtained, and are intended to gather additional information to evaluate the overall benefit-risk relationship of the drug and provide an adequate basis for physician

labeling(ClinicalTrials.gov & FDA)

- Phase IV trials studies of FDA-approved drugs to delineate additional information including the drug's risks, benefits, and optimal use(ClinicalTrials.gov & FDA)
- VII.B.2 Does this project involve a drug washout (asking subject to stop taking any drugs s/he is currently taking)?
 No
- VII.B.6 Will any subjects receive a placebo in this study when, if they were not participating, they could be receiving an FDA-approved treatment for their condition?

 No
- VII.B.11 Is there a separate, written protocol that will be submitted in addition to this IRB New Project form? (Note: a grant application is not considered to be a protocol)

 No
 - VII.B.18 Does this project involve the evaluation, or testing, of the safety and/or efficacy of a medical device? Yes
 - VII.B.19 Describe in detail procedures in place for maintaining device shipment and receipt records:

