The Principal Investigator will identify subjects that meet inclusion criteria based on chart review prior to potential subjects' upcoming glaucoma clinic appointments. Potential subjects will be approached at the time of their scheduled appointment to participate in the study. The Principal Investigator and/or research assistant will describe the purpose of the study, study procedure, and risks/benefits of participation prior to obtaining informed consent from the subject. Additionally, the Principal Investigator and/or research assistant will reassure potential subjects that their participation in the study is completely voluntary, they are free to withdraw from the study at any point without consequences, and their decision to participate/not participate will not affect their regular care.

VII.D.37 Does the study include any form of deception (e.g., providing participants with false information, misleading information, or withholding information about certain study procedures)?

Examples:

- Procedure includes a cover story that provides a plausible but inaccurate account of the purposes of the research.
- Participants will be provided with false information regarding the particular behaviors of interest in the research.
- Procedures include a confederate pretending to be another participant in the study.
- Participants will be told that the research includes completion of a particular task, when in fact, that task will not be administered.
- Study is designed to introduce a new procedure (or task) that participants are not initially told about.
- If yes, a waiver of informed consent must be requested under question IV.3.

No

VII.E. Project Description (E)

- VII.E.1 Will subjects be randomized?
 - VII.E.1.a Will any subjects be blinded to which study arm they have been assigned?
 No
 - VII.E.2 Describe randomization scheme/assignment including ratio such as 1:1, 2:1 etc.
 Patients will be randomized in a 1:1 ratio to either perform Humphrey Visual Field testing followed by Smart System VR Headset testing or vice versa.
- VII.E.3 Will any questionnaires, surveys, or written assessments be used to obtain data directly from subjects in this study?
 Yes

- VII.E.4 List all questionnaires, surveys, written assessments and ATTACH each one to the application. (NOTE: You are NOT prohibited from attaching copyrighted materials to this application)
 Smart System VR Headset satisfaction survey

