- VII.E.5 Does this project involve creating any audiotapes, videotapes, or photographs?
- VII.E.6 Provide a detailed description in sequential order of the study procedures following the consent process DO NOT cut and paste from the Consent Document.

Describe study populations separately if they will be participating in different procedures - include CONTROL population if applicable.

DESCRIBE:

- What subjects will be asked to do/what happens in the study (in sequential order)
- The time period over which procedures will occur
- The time commitment for the subject for individual visits/procedures
- Long-term followup and how it occurs

Potential subjects will be approached at the time of their regularly scheduled appointment to participate in this research study. The research assistant will answer any questions potential subjects may have regarding the purpose, procedure, and risks of the study. If they agree to participate, subjects will sign an informed consent.

In addition to routine clinical examination including measurement of visual acuity, tonometry, and slit lamp examination, subjects will undergo perimetry with both the Smart System VR Headset (SSVR) and the Humphrey Field Analyzer (HFA). If the subject requires pupillary dilation during their appointment, visual field testing (VF) will be conducted prior to dilation. Subjects will be randomized to perform either the SSVR VF followed by the HFA VF or vice versa. Both VF will occur on the same day with a 15-20 minute break between tests at the University of Iowa Hospitals and Clinics' Glaucoma clinic. The total additional time commitment of study participation is expected to be 1-2 hours.

The SSVR Headset uses a 24-2 examination protocol with a Neighborhood-Zippy Estimation by Sequential Testing (ZEST) testing algorithm. Background brightness will be set to 15.8 ASB. The test will use Goldmann size III stimulus. The research assistant will administer the SSVR VF. The SSVR VF will be deemed unreliable if FP >25%. The HFA uses a 24-2 examination protocol with a SITA standard testing algorithm. A clinical technician will administer the HFA VF. The HFA VF will be deemed unreliable if FP >15%. After completing both VF tests, subjects will complete a satisfaction survey regarding the SSVR.

VII.E.7 Will you attempt to recontact subjects who are lost to follow-up?

No - those lost to followup will not be recontacted

VII.E.9 Will subjects be provided any compensation for participating in this study?

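### Test order is randomised, but the visible analysis carries no period term; a smaller point is that the rest between tests is given as both one hour and 15-20 minutes

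*Combined protocol and SAP*

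**What the plan says.** **Order and analysis.** VII.E.2 says "Patients will be randomized in a 1:1 ratio" to the Humphrey test then the headset, or the reverse. XI.1 names pointwise comparisons grouped by the Garway-Heath map. XI.2 anticipates a mixed-model test at the 0.05 level. It mentions order once, calling the two orders cluster one and cluster two, and it lists no model terms. It also refers to a full power calculation attached to the IRB form, which is not among the documents.

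**Rest interval.** I.4, the lay summary, says "Visual field tests will be separated by a rest period of one hour to minimize testing fatigue". VII.E.6, the detailed procedure, says "Both VF will occur on the same day with a 15-20 minute break between tests". The added time for the subject is 1.5-2 hours in I.4 but 1-2 hours in VII.E.6 and VIII.1. VII.B.11 asks "Is there a separate, written protocol that will be submitted in addition to this IRB New Project form", and the answer is no, so nothing else is cited that would settle the interval.

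**The concern.** The plan itself treats fatigue as a threat to the second test: I.4 gives it as the reason for the rest. Randomising the order lets the analysis separate a second-test effect from the device effect, but only if the model has a term for it. Without one, subjects in one order show the device difference minus the second-test effect and subjects in the other show it plus that effect. The analysis then counts this predictable spread as noise. At stake is the width of the interval for the device difference, overall and in each sector.

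The use of the word cluster for test order does not fill the gap. A label for order is not a first-or-second-test effect, and two orders do not match the 40 clusters per device in the same paragraph.

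The rest interval is a smaller matter. Two current passages give values that do not overlap for the same break, and the only stated purpose, limiting fatigue, is attached to the longer one.

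**Working it through.** **The plan's own figure.** XI.2 states 87% power with 80 per device, clusters of 2, SD 0.25 and ICC 0.5. The detectable difference reads as 0 and looks cut off, so the figure cannot be reproduced directly. Solving back, with a two-sided test assumed:
- effective n per device = 80 / (1 + 0.5) = 53.3
- difference = (1.960 + 1.126) × 0.25 × √(2/53.3) = 0.149

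So 87% fits a difference near 0.15, which the documents cannot confirm. Nothing below depends on it.

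**Inputs for the period term.**
- Two orders, 1:1 (VII.E.2).
- n = 52, the expected enrolment in VI.1.
- n = 40, an assumption: the 40 clusters in XI.2 read as 40 subjects tested on both devices.
- Second-test effect π of 0.25 or 0.5 times s, where s is the SD of the subject-level paired difference. These are assumptions; the documents give neither π nor s.

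**Effect of omitting period, balanced orders.** With device difference τ, the paired difference has mean τ − π in one order and τ + π in the other.
- Mean over balanced orders: τ, so no bias.
- Variance used by the analysis: s² + π².
- Interval width ratio: √(1 + (π/s)²).
  - π = 0.25 s: √1.0625 = 1.031, about 3% wider.
  - π = 0.5 s: √1.25 = 1.118, about 12% wider.

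A simulation of 40,000 trials with orders 20:20 gives ratios of 1.031 and about 1.12, with absolute bias below 0.002 SD.

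**Chance imbalance.** If randomisation is unblocked, the imbalance has mean zero over repeated trials. Simulating 40,000 trials at n = 52 with period omitted gives mean bias below 0.002 SD and 95% interval coverage of 0.950 and 0.951 for the two effects. The wider interval already covers this imbalance.

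**Cost of the term when π = 0.**
- 20:20: t(0.975, 38) / t(0.975, 39) = 2.0244 / 2.0227 = 1.0008.
- 26:26: t(0.975, 50) / t(0.975, 51) = 2.0086 / 2.0076 = 1.0005.
- 26:20 (an assumed loss of 6 from one order): √(46 × (1/26 + 1/20) / 4) × t(0.975, 44) / t(0.975, 45) = 1.0086 × 1.0006 = 1.009.

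**Rest interval, side by side.**

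| | I.4 | VII.E.6 |
|---|---|---|
| Rest between tests | 60 minutes | 15-20 minutes |
| Added time | 1.5-2 hours | 1-2 hours |

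The gap is 60 − 20 = 40 to 60 − 15 = 45 minutes. Its effect on fatigue is not given and is not estimated here.

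**The case against.** **The attachment may answer it.** XI.2 lists no model terms at all, so the missing period term may be part of a brief description, not a decision to leave it out. This stands, and the recommendation is conditional for that reason.

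**No bias has been shown.** A reader might infer that the device comparison is biased because period is omitted. The documents do not support this. Balanced orders give no bias, and chance imbalance gives none on average and is covered by the unadjusted interval. Quoting a shift from chance imbalance on top of the wider interval would count the same thing twice.

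**Exclusions could unbalance the orders.** A reader might also point to the two reliability rules in VII.E.6, "The SSVR VF will be deemed unreliable if FP >25"% and "The HFA VF will be deemed unreliable if FP >15"%, and infer bias from exclusions. But the text calls such fields unreliable without saying they are dropped. Every subject also takes both tests, so different cut-offs alone cannot favour one order; false-positive rates would have to depend on order too. This remains a possibility, not a finding.

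**The rest conflict is close to clerical.** This also stands. I.4 is a lay summary, the study runs at one clinic, and staff have a detailed procedure to follow in VII.E.6. A reader might infer that the conflict leaves fatigue uncontrolled or lowers power; nothing in the documents shows either.

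**Conclusion.** The point holds as a cheap improvement in precision plus a minor consistency correction. The visible analysis does not use the randomised order to remove a second-test effect. For assumed effects of 0.25 or 0.5 SD of the paired difference, the interval is about 3% or 12% wider than it need be with balanced orders. These figures assume that the second-test effect is the same on either device. They are illustrations, since the documents give no effect size. Systematic bias would arise only if analysed subjects were lost differentially by order, which the documents do not show.

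The rest interval is a real contradiction in current text, 60 against 15-20 minutes, with no effect on sample size or power claimed. Neither part puts the study's validity in doubt.

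**What to change.** 1. **Period term.** State in XI.1 and XI.2 that the device comparison includes test period (first or second test) as a fixed effect, unless the attached calculation already does so. Apply it both in the mixed model and in the sector-level pointwise comparisons, which are the analysis XI.1 actually names. The cost is one degree of freedom in each comparison and no new data. With no period effect, the interval is under 0.1% wider if orders are balanced and about 0.9% wider at 26:20.
2. **Rest interval.** Give one value in I.4 and VII.E.6, the same for both test orders. By default correct I.4 to 15-20 minutes, because VII.E.6 is the detailed procedure, and align the time commitments in I.4, VII.E.6 and VIII.1. This is a wording change. If one hour is preferred, it adds up to 40-45 minutes per subject to the VII.E.6 schedule, less any routine examination done during the rest.

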 The Department of Ophthalmology already owns a Smart System VR Headset, so no additional device will need to be ordered/shipped/received.
 - VII.B.20 Who will be responsible for maintaining these shipment and receipt records?

 The Department of Ophthalmology already owns a Smart System VR Headset, so no additional device will need to be ordered/shipped/received.
 - VII.B.21 Describe in detail procedures in place for tracking use and disposition of devices described in this study:

 The Smart System VR Headset is stored in a locked office in the University of Iowa Hospitals and Clinics'

 Department of Ophthalmology. The device will only be accessed by key personnel of the study. Device usage is automatically recorded upon test completion, so no additional physical record will be maintained.
 - VII.B.22 Who will be responsible for maintaining these use and disposition tracking records?

 Key personnel of the study, including the PI and research assistants, will be responsible for the testing data and, therefore, the "disposition tracking record".
 - VII.B.23 Describe in detail procedures in place to limit access to authorized study personnel for the storage, control, and dispensing of the investigational devices. (For example, investigational devices are kept in a locked area away from approved devices or have a keyed interlock, and only study personnel authorized to dispense the device have the keys)

The Smart System VR Headset will be stored in a locked office in the University of Iowa Hospitals and Clinics' Department of Ophthalmology. Only study personnel authorize to use the device will have access to this office.

- VII.B.24 Is the device FDA-approved for the way it will be used in this study?
 - VII.B.25 Is there an IDE (Investigational Device Exemption) for this device in this research project?

 No
 - VII.B.29 Indicate the appropriate FDA status you and/or the sponsor are requesting for the use of this device in this study.

Non-Significant Risk (NSR) device/software

VII.B.31 Provide a detailed rationale for why this device meets the FDA definition of a Non-Significant Risk Device (NSR)

Per M&S, the Smart System VR Headset is "Class I" and doesn't need FDA Approval (highest-risk like neurostimulators) or FDA Clearance (medium-risk devices / 510(k)). They include it in their device listings on the FDA Establishment Registration (screen prints attached to additional documents section).

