
No

VIII. Risks

VIII.1 What are the risks to subjects including

- emotional or psychological
- financial
- legal or social
- physical?
- -Loss of time (expected study commitment is 1-2 hours)
- -Loss of confidentiality
- -Minor risk of physical discomfort due to experimental headset weight and security strap
- VIII.2 What have you done to minimize the risks?
 - If applicable to this study ALSO include:
 - How you (members of your research team at Iowa) will monitor the safety of individual subjects.
 - Include a description of the availability of medical or psychological resources that subjects might require as
 a consequence of participating in this research and how referral will occur if necessary (e.g. availability of
 emergency medical care, psychological counseling, etc.)

Patient privacy will be protected by separating patient identifiers from the data and storing the data on a password-protected computer in a locked office within the Ophthalmology Department. To prevent a loss of confidentiality from occurring, all data will be located on a UIHC encrypted, password-protected Department of Ophthalmology server. Only designated research team members and PI will have access to the drive. Any paper documents will be kept in a locked file cabinet in the principal investigator's office.

M&S Technologies receives subject demographic and testing data upon completion of testing using the Smart System VR Headset. This data is stored in a secure, encrypted, HIPAA-compliant database. Subject names are not stored. Instead, Subjects receive encrypted ID codes. Subject data is only shared with M&S-affiliated consultants and service providers, healthcare providers using the Smart System VR Headset, and for law enforcement and judicial proceedings are permitted by law.

The study utilizes data generated as a consequence of routine clinical practice, as well as an additional in-clinic visual field test. The study poses no therapeutic questions and no interventions; no treatment is directed by the study. Therefore, the study poses no substantive risk to the patient other than loss of time and confidentiality. It does not impose any significant burden on the patient.

VIII.3 Does this study have a plan to have an individual or committee review combined data from all subjects on a periodic basis (such as summary or aggregate safety and/or efficacy data)?

No

IX. Benefits

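### The Aim 2 survey and the headset use record both follow test completion, and nothing is written for subjects who stop early, so ease of use may be summarised in completers only

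*Combined protocol and SAP*

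**What the plan says.** **The aim.** I.5 states "Aim 2: Determine the subjective perception of ease of use of the Smart System VR Headset". VII.E.4 lists one instrument, the headset satisfaction survey.

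**When the survey is given.** VII.E.6: "After completing both VF tests, subjects will complete a satisfaction survey regarding the SSVR". The summary in I.4 puts it at the same point: "Following visual field testing using both the Smart System VR Headset and Humphrey Field Analyzer, subjects will complete a 13-question satisfaction survey".

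**What records headset use.** VII.B.21: "Device usage is automatically recorded upon test completion, so no additional physical record will be maintained". VII.B.22 treats the testing data as the tracking record. The transfer to the manufacturer has the same trigger (VIII.2): "M&S Technologies receives subject demographic and testing data upon completion of testing using the Smart System VR Headset".

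**The risk and the right to stop.** VIII.1 lists "Minor risk of physical discomfort due to experimental headset weight and security strap". VII.D.29 tells subjects that "they are free to withdraw from the study at any point without consequences". VII.E.7 says that those lost to follow-up are not recontacted.

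**Analysis.** XI.1 names the survey among the variables to be analysed. The only method it describes is the pointwise field comparison. It gives no method for the survey and no rule for subjects without one.

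**The concern.** A subject who takes the headset off because it is heavy, slips or is confusing has stopped for the very reason that Aim 2 is meant to measure. Followed step by step, the written procedure brings that subject to neither the survey nor the device's log. The missing data would then be related to the outcome, and a summary of completers would lean in the headset's favour.

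Comfort is part of the case for the device. I.6 cites the difficulty some patients have in positioning themselves at the Humphrey, and IX.2 expects that the headset may reduce discomfort. VII.B.32 reports no prior studies of it, so the plan offers no outside tolerability figure to set beside the result. For Aim 1, a comparison of fields among completers is easier to interpret when the share unable to finish each test is reported next to it.

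**Working it through.** The plan gives no figure for early stopping or for expected survey results, so there is nothing to reproduce. The check is a reading of the text, followed by an illustration on assumed rates.

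**1. What each kind of subject leaves behind, following the text as written**

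| Subject | Device use record | Survey | Reason for stopping |
|---|---|---|---|
| Completes both tests | yes | yes | not applicable |
| Starts the headset test and stops | none described | none described | none described |
| Headset first, finishes it, then stops the Humphrey | yes | none described | none described |

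The third row arises because the survey concerns the headset but comes after both tests.

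**2. What can still be recovered.** Every subject signs a consent (VII.E.6) and every completed headset test is logged (VII.B.21). So

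subjects without a completed headset test = consents − subjects with a completed test.

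This count covers every cause, including subjects who never put the headset on, and it carries no reasons. If all 52 planned subjects (VI.1) had completed tests, 0/52 could be reported, with a one-sided 95% upper bound of 1 − 0.05^(1/52) = 5.6%.

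**3. Chance that someone is affected.** Let d be the share of headset starters who stop; d is assumed. With N = 52, expected stops = 52d and P(at least one) = 1 − (1 − d)^52.

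| d | Expected stops | P(at least one) |
|---|---|---|
| 2% | 1.04 | 65% |
| 5% | 2.6 | 93% |
| 10% | 5.2 | 99.6% |

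I.4 gives 50 subjects instead of 52, which hardly changes these values.

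**4. Effect on Aim 2.** Let c be the share of completers who are favourable and f the share of stoppers who would be.

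- Completer summary: c
- All headset starters: c(1 − d) + fd
- Overstatement: c − [c(1 − d) + fd] = d(c − f)

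Take c = 80% (assumed).

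| d | f = 0% | f = 40% | f = 80% |
|---|---|---|---|
| 0% | 0 | 0 | 0 |
| 2% | 1.6 points | 0.8 | 0 |
| 5% | 4.0 points | 2.0 | 0 |
| 10% | 8.0 points | 4.0 | 0 |

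The f = 0% column is the extreme case, in which no stopper would have rated the headset favourably. The overstatement shrinks as stoppers come to resemble completers, and it vanishes if nobody stops.

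**The case against.** A reader might infer that early stoppers are excluded from the survey by rule. The documents do not support that. VII.E.6 answers a prompt asking for procedures in sequence, so its sentence fixes the survey's place in the usual order. I.4 says only that the survey follows testing. Neither bars surveying someone who stops; the form is silent on such subjects.

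A reader might also infer that stops would be invisible, or that VII.B.21 forbids staff from noting them. That section concerns device accountability. The research assistant who administers the headset test would see a stop, and the count follows from consents minus completed tests. Only the reasons, and any commitment to report the count, are missing.

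Nor can it be said that discomfort goes unmeasured altogether. The 13 survey questions are an attachment that is not shown, and they may cover it for those who complete the survey.

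Finally, stopping may be rare. The headset test is expected to take about 5 to 10 minutes, the strap is adjustable, VIII.1 calls the risk minor, and VI.13 excludes neurocognitive or psychiatric patients who cannot perform testing. These points bear on the size of the problem and should temper it. They do not supply a survey offer or a recorded reason for a subject who does stop.

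**Conclusion.** The point stands as a gap in what is written down, and it is cheap to close. If any subject stops because of discomfort or difficulty with the headset, the procedure as written leads to an Aim 2 summary in completers, which would tend to be too favourable, with no recorded reason for the stop.

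The size cannot be determined from the documents. At assumed stopping rates of 2%, 5% and 10% the overstatement is 1.6, 4.0 and 8.0 percentage points. Those figures rest on 80% favourable among completers and no stopper favourable. The overstatement is smaller if some stoppers would have been favourable, and zero if no one stops. Bias in Aim 2 is therefore a possibility that the plan leaves open, not an established result.

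**What to change.** - **VII.E.6:** offer the survey to every subject on whom the headset is placed, including anyone who stops either test early. It must remain an offer and not a condition of withdrawal, since VII.D.29 lets subjects leave freely.
- **VII.B.21:** have the research assistant keep one line per headset start, recording whether the test was completed, the reason for stopping if given, and any discomfort.
- **XI.1:** report the number and share of subjects not completing each device's test. Present Aim 2 with all headset starters as the denominator, and show survey non-response as its own category so that declined surveys stay visible.

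The cost is a modification of the form and a one-line log kept by someone already present. Ease-of-use figures may look slightly less favourable. Reasons for stopping are hard to recover afterwards, so the log has to be in place while subjects are being tested.
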